19.0 Adverse Event Reporting

20.0 Study Monitoring, Auditing and Inspecting

21.0 Future Undetermined Research: Data and Specimen Banking

22.0 References

1.0 Objectives

1.1 Study Objectives

The **primary objectives** of this study are to define the extent of dermatomal anesthesia and anatomical spread of injectate (as defined by MRI imaging) that is provided by an ESP block at the T5 level, using twenty milliliters of 0.5% ropivacaine. MRI data will not be collected after May 2023

The **secondary objectives** include: 1) the measurement of changes in hemodynamic parameters associated with the ESP block, 2) the duration of sensory effects provided by ropivacaine with or without epinephrine, 3) the venous plasma concentration of ropivacaine at various time intervals after completion of the ESP block.

1.2 Primary Study Endpoints

Outcomes to be assessed

1. Extent of dermatomal sensory loss
2. Duration of sensory loss
3. Anatomical extent of injectate spread using MRI imaging. MRI data will not be collected after May 2023
4. Venous plasma concentration of ropivacaine at periodic time intervals

We are comparing these outcomes between

1. 20ml ropivacaine 0.5% with epinephrine vs no epinephrine

1.3 Secondary Study Endpoints

1. Hemodynamic parameters at periodic time intervals
2. Any adverse effects or side effects related to injection of the medications

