3.3 Early Withdrawal of Subjects

3.3.1 Criteria for removal from study

- Subject does not complete the study
- Develop any complications or side effects due to injections.
- Abnormal Creatinine level following baseline blood test
- Subject does not follow fasting rules

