3.3.2 Follow-up for withdrawn subjects

Any subject withdrawn from the study due to complications or side effects of the injection will be seen immediately by the PI and a course of treatment will be determined.

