7.1.1 Randomization process

The subjects enrolled will be randomized into two groups (6 participants in each group) by a computer-generated randomization list using SAS software (SAS Institute, Cary, NC):

Randomization groups

1. Group RE will have 20mL of **0.5% Ropivacaine with epinephrine** injected at the left or right T5 transverse process.
2. Group R will have 20mL of **0.5% Ropivacaine without epinephrine** injected at the left or right T5 transverse process.

The randomization will be performed, using a sealed envelope technique, and will be stratified according to the side of the injections (either left or right) so that each arm will have equal number of left and right sided ESP blocks. This will be done by the investigational pharmacy while preparing the medications. All subjects, the anesthesiologist performing the procedure, the radiologist, and the research coordinator collecting the data will be blinded and will not be aware of the details of the injection and allocation of the participants. In the event that the patient has a concerning reaction or becomes unstable in any fashion, the patient will be immediately unblinded and removed from the study.

The conduct of the study will be as follows.

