Once the final sensory assessment has been completed (360 minutes following block), the subject will remain for an additional 30 minutes of observation. The intravenous cannula will be removed and the subject will then be discharged to return home. The subjects will be discharged from the research facility with a note to inform the PI or Research coordinator if they feel anything different or abnormal. The subject should not drive for 24 h after receiving the block, and will need to have someone to drive them home after the procedure.

7.3

Duration of Participation

It will take three days to complete this research study. For two consecutive days following the procedure they will be asked to participate in a follow-up phone call to discuss how they are feeling. The script for the follow-up phone call is attached.

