10.0 Data and Safety Monitoring Plan

10.1 Periodic evaluation of data

The PI and research coordinator will review cumulative adverse events, early termination of study participation, and accrual every six months and report any issues requiring modification of the study or alteration of the risk: benefit ratio to the IRB immediately. A summary of adverse events, study progress and protocol modifications will be included for IRB review in the continuing review.

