10.2 Data that are reviewed

The data to be reviewed will be:

- Safety data
- Untoward events
- Efficacy data

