10.3 Method of collection of safety information

Safety information will be collected by the research coordinator at study visits and follow-up phone call.

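### Endpoint 1.3(2) counts adverse effects only if related to the injection, although safety data are collected without that condition; an all-event count in all injected subjects would be a cheap improvement

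*Combined protocol and SAP*

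**What the plan says.** The second secondary endpoint in 1.3 is "Any adverse effects or side effects related to injection of the medications". Section 1.3 does not say who decides whether an effect is related, by what criteria, or when.

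Collection and review are wider:

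- Section 10.3: "Safety information will be collected by the research coordinator at study visits and follow-up phone call".
- Section 7.3: "For two consecutive days following the procedure they will be asked to participate in a follow-up phone call to discuss how they are feeling". At discharge, subjects are also asked to report anything that feels unusual (7.2).
- Section 10.1, repeated in 10.6: "The PI and research coordinator will review cumulative adverse events, early termination of study participation, and accrual every six months".
- Section 10.2 lists "Untoward events" among the data reviewed.

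Two rules take subjects out of the study. Section 3.3.1 gives as a removal criterion "Develop any complications or side effects due to injections". Section 7.1.1, repeated in 7.4.5, says that a subject who "has a concerning reaction or becomes unstable in any fashion, the patient will be immediately unblinded and removed from the study". On what follows, 3.3.2 says "Any subject withdrawn from the study due to complications or side effects of the injection will be seen immediately by the PI", with treatment then decided. It does not mention the follow-up calls.

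Section 8.2 describes a pilot whose results are descriptive. Section 8.3 covers MRI measurements and dermatomal anesthesia, and sets out no adverse-event summary.

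**The concern.** A relatedness condition inside a safety endpoint makes the count depend on a causal opinion. In a small first description of a technique that opinion is hard to form. Section 11.0 itself says that the safety of the procedure is not fully known. A reader who sees zero events cannot tell whether nothing happened or something happened and was judged unrelated.

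Two features of the plan sharpen this. First, immediate unblinding after a concerning reaction means that attribution may be made by someone who knows the arm. The arms differ essentially only in epinephrine (7.4.1), and 11.0 lists fast heartbeat, headache and dizziness as epinephrine effects, so knowing the arm could colour the judgement. Second, the subjects who react are the ones removed, and the plan does not say that their day 1 and day 2 safety information is still collected.

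At stake is the completeness of one descriptive count that may inform the larger trial foreseen in 8.2.

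**Working it through.** The plan states no figure for this endpoint, so there is none to reproduce. The check sets the sections side by side and follows events through them.

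**Step 1. Where does relatedness appear?**

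| Place | Purpose | Relatedness required? |
|---|---|---|
| 1.3(2) | Endpoint | Yes |
| 7.2, 7.3 | Subject reports, follow-up calls | No |
| 10.1, 10.2, 10.6 | Review of data | No |
| 10.3 | Collection of safety information | No |
| 3.3.1 | Removal from study | Yes (due to the injection) |
| 19.1 | Reporting to the IRB | Yes (unexpected and probably related) |

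The endpoint is therefore narrower than the data collected.

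**Step 2. An event reported at the day 1 call.** It is collected (10.3) and reviewed (10.1). If judged related, it enters 1.3(2). If judged unrelated, it does not, although it stays in the study record.

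**Step 3. A concerning reaction on the day of the block.** The subject is unblinded and removed (7.1.1). Any attribution made after that point is made with the arm known. The plan does not require attribution to be recorded before then.

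**Step 4. A subject removed under 3.3.1.** The event is by definition due to the injection, so the relatedness condition cannot exclude it. What is open is different: whether the subject still gets the two calls. Section 3.3.2 speaks only of being seen and treated. The schedule in 10.4 lists the calls without saying whether removed subjects receive them.

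**Step 5. Can the chance of an omission be computed?** With p the chance that a subject has a given symptom and q the share of such events judged unrelated, the chance of at least one omission among 12 injected subjects is 1 − (1 − p·q)^12. Section 11.0 gives p only in bands, such as 5% or greater for headache and nausea with ropivacaine. It gives nothing for q. At p = 5%, letting q run from 0 to 1 takes the result from 0% to 1 − 0.95^12 = 46.0%, and p may exceed 5%. That range carries no information. These symptoms are also listed as drug effects, which favours calling them related. No probability is claimed here.

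**Step 6. Scale of one omission.** Six subjects per group (7.1.1). With exact (Clopper-Pearson) 95% limits:

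- event counted: 1/6 = 16.7%, limits 0.4% to 64.1%;
- event omitted: 0/6 = 0%, upper limit 1 − 0.025^(1/6) = 45.9%.

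Each subject is worth 16.7 percentage points of an arm's rate. The intervals overlap widely, so the gain from the fix is a complete count and not precision.

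**The case against.** The endpoint begins with the word any and names no judge, criterion or threshold. Where the protocol wants a causal opinion it says so, as in 19.1. The phrase may only mark scope, and could even be read as qualifying side effects alone. Nothing recorded is lost: collection is unfiltered, and a summary of adverse events goes to the IRB (10.1). Choosing injection-related effects as an endpoint is legitimate. Acute reactions that trigger unblinding are the hardest to call unrelated, and a serious one suspends the study (10.8).

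Much of this stands. The current wording is a defensible choice, and the record is complete. But the natural reading applies the condition to both kinds of effect, and the IRB summary is a monitoring report, not the endpoint. An endpoint that depends on relatedness without saying who judges it, or when, is open to inconsistent use.

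Three stronger readings may tempt a reader:

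- *Removed subjects will be left out of the safety results.* No section says so. The figure of 12 who complete (8.1) is a recruitment target, not an analysis set. Leaving out those removed under 3.3.1 would nearly empty the endpoint, which makes that intention unlikely.
- *Injected subjects who are removed will be replaced, changing the denominator.* No such replacement is described. The allowance up to 35 is for people who never receive the block.
- *The comparison of arms is biased.* The stated comparison with and without epinephrine sits under the primary endpoints (1.2), and 8.3 plans no test of adverse effects.

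**Conclusion.** The point holds in a limited form. As worded, 1.3(2) leaves out events that are collected but judged unrelated, and after a concerning reaction that judgement may be made unblinded. The removal rules take out subjects with reactions without stating that their day 1 and day 2 calls continue.

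This rests on reading the relatedness phrase as a condition on both kinds of effect, and on expecting a descriptive summary by arm, which the pilot purpose in 8.2 suggests but 8.3 does not set out. How often an event would be omitted is unknown. The only size that can be given is that one omitted subject moves an arm from 1/6 to 0/6.

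The effect is confined to one descriptive secondary endpoint in 12 volunteers. No test, sample size, IRB reporting, subject oversight or the hemodynamic endpoint depends on it. It is an optional improvement, not an error.

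**What to change.** - In 1.3(2), define the endpoint as any adverse event from needle insertion to the day 2 follow-up call, whether or not judged related.
- In 8.3, say that it is reported descriptively by arm, as the number of subjects with each event out of all injected subjects.
- Show the investigator's attribution as a column and not as a condition for being counted. Record it before unblinding where possible, and flag it if made after. Unblinding for the subject's safety should not wait for it.
- State in 3.3.2 that subjects removed or unblinded for a reaction stay in the safety count and still receive both calls.

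The cost is a few sentences and one table column with a flag. No new visit or assessment is needed, since both calls are already scheduled. The downside is that some minor unrelated complaints will appear in the table.

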2.0 Background

2.1 Scientific Background and Gaps

Thoracic surgery is associated with significant postoperative pain and providing adequate analgesia in these patients is essential for enhanced recovery protocols¹. Regional anesthesia

techniques, such as thoracic epidural and thoracic paravertebral blockade, are therefore commonly employed². These techniques have limitations however; they require a high degree of technical expertise, are contraindicated if the patient has a coagulopathy, and are associated with significant adverse effects and risk of complications. These include, but are not limited to hypotension, pneumothorax, and epidural abscess or hematoma formation. We recently described a novel ultrasound-guided regional anesthetic technique for providing thoracic analgesia, the ultrasound-guided Erector Spinae Plane (ESP) block. The ESP block involves injection of local anesthetic into the musculofascial plane deep (anterior) to the erector spinae muscle and superficial (posterior) to the tip of the transverse processes of the thoracic spine. Our radiological and anatomical investigation in fresh adult cadavers has shown that injection of a clinically-relevant volume (20ml) at the T5 vertebral level produces extensive spread of injectate within the erector spinae musculofascial plane, along the Para spinal and posterior chest wall, and extending between C4 and T12 vertebral levels³. This corresponds with early clinical experience indicating that the ESP block is effective in treating chronic thoracic pain³, acute post-thoracic surgical pain⁴⁻⁶, and pain from rib fractures⁷. It thus appears to provide similar analgesia to a thoracic paravertebral block, while being technically simpler and safer to perform. The ESP block therefore has promise as a simple, safe, yet highly effective method of providing thoracic analgesia, and one that can be learned and performed by the majority of anesthesiologists.

2.2 Previous Data

Ultrasound-guided ESP injections of a clinically relevant volume (20 mL) of normal saline (with iodinated contrast and methylene blue) at the T5 vertebral level were performed in fresh cadavers. The cadavers underwent computed tomography imaging and anatomical dissection. The radiological and anatomical findings demonstrated a distribution of injectate within the erector spinae musculofascial plane, along the Para spinal and posterior chest wall, and extending between C4 and T12 vertebral levels [4]. It is unclear how the extent of spread may have been influenced by the state of preservation of the cadaver, post mortem tissue desiccation, temperature difference, and lack of perfusion and respiratory motion that would be present in a living subject. Even though the ESP block has not been studied extensively for evaluation of mechanism of action, there are a number of case reports and case series that have been published in the last year, where ESP has been shown to be safe in different conditions of use. [4-6] To date, there are 39 manuscripts that have been published and indexed in PubMed, and no associated complications or side effects have been reported. A list of those publications can be found using the following link:

<https://www.ncbi.nlm.nih.gov/pubmed/?term=erector+spinae+plane+block>. Here at the Penn State Hershey Medical Center, more than two hundred of these blocks have been performed for different procedures, without any complications or side effects.

2.3 Study Rationale

At present, no systematic investigation has been published that describes first, the spread of injectate following the ESP block in live human subjects; second, the extent of sensory blockade that can be reliably expected; and third, the pharmacokinetics of local anesthetic injected into this location. It is also unknown what effect additives such as epinephrine, might have on these parameters. Epinephrine is commonly used for erector spinae plane blocks (ESP) or similar peripheral fascial plane injections to produce local vasoconstriction in order to prolong the action of the ropivacaine. The current evidence for the mechanism of action and efficacy of the ESP block in providing sensory blockade of the thorax comes from cadaveric studies and small patient case series.[4-6] For this potentially valuable regional anesthesia technique to be adopted more widely in clinical practice, it is essential to determine, with more precision, the mechanism of action in live human subjects, and the extent of sensory blockade that can be reliably achieved

with clinically significant volumes of injectate boluses. Local anesthetic systemic toxicity, although rare, is always a concern in regional anesthesia and it is, therefore, also important from a safety perspective to determine the pharmacokinetics associated with the ESP block, so as to provide appropriate guidelines for maximum dose, volume and concentration of local anesthetic to be injected. In addition, this knowledge will provide baseline data from which to embark upon comparative studies with other more established techniques for regional anesthesia of the thorax, such as thoracic epidural or thoracic paravertebral blocks. A volunteer study in non-anesthetized subjects offers the most controlled setting to study these factors, as it eliminates the confounding effects of concomitant analgesic and anesthetic medications, surgical trauma, and patient co-morbidities.

3.0 Inclusion and Exclusion Criteria

3.1 Inclusion Criteria

- Healthy adults, male or female, aged 18 to 60 inclusive
- Weight between 55 and 100 kg inclusive
- Height 160 to 190 cm inclusive
- Normal baseline creatinine result

3.2 Exclusion Criteria

- Pregnant females
- Chronic medical condition requiring medication
- History of previous major spinal, abdominal or thoracic surgery
- Congenital abnormalities of the spine, back, thorax or abdomen
- History of major trauma to the thorax or abdomen;
- Allergy to ropivacaine or other amide local anesthetics
- The presence of any metallic implant in their body
- Any contraindication to magnetic resonance imaging as determined by completion of a standard questionnaire administered to all patients undergoing magnetic resonance imaging. (Does not apply after May 2023)
- Individuals with any clinically relevant history or the presence of neurological deficits or cardiovascular disease
- Trainees actively involved within the Department of Anesthesiology (e.g., fellows, students and residents)

3.3 Early Withdrawal of Subjects

3.3.1 Criteria for removal from study

- Subject does not complete the study
- Develop any complications or side effects due to injections.
- Abnormal Creatinine level following baseline blood test
- Subject does not follow fasting rules

3.3.2 Follow-up for withdrawn subjects

Any subject withdrawn from the study due to complications or side effects of the injection will be seen immediately by the PI and a course of treatment will be determined.

4.0 Recruitment Methods

4.1 Identification of subjects

We will hang recruitment flyers

4.2 Recruitment process

Healthy volunteers aged between 18yrs to 60 of both genders will be recruited with Recruitment Flyers. Interested subjects will be interviewed by the project coordinator from the Department of Anesthesia over the phone and will be advised to meet them at the Anesthesia clinic at a scheduled time. The informed written consent for the study will be obtained from them at the Anesthesia Clinic.

4.3 Recruitment materials

- Recruitment Flyer

4.4 Eligibility/screening of subjects

Interested subjects will be interviewed by the project coordinator from the department of Anesthesia over phone using the attached IRB approved phone script and will be advised to meet them at the Anesthesia clinic at a scheduled time.

5.0 Consent Process and Documentation

5.1 Consent Process

5.1.1 Obtaining Informed Consent

5.1.1.1 Timing and Location of Consent

Consent to participate will be obtained from eligible patients after preoperative evaluation in the Anesthesia Preoperative Evaluation Clinic (APEC), during this visit blood will be drawn and sent to the clinical laboratory for measurement of kidney function as base line creatinine level. If the creatinine level is higher than normal they will be informed about it and excluded from the study.

5.1.1.2 Coercion or Undue Influence during Consent

The patient will be advised that participation in research studies is voluntary and that their decision to participate or not participate will not affect the level of care at this institution.

5.1.2 Waiver or alteration of the informed consent requirement

Not applicable

5.2 Consent Documentation

5.2.1 Written Documentation of Consent

We will obtain a consent form signed by the patient and the person obtaining the consent. An original signed copy will be retained by the patient and the research team and a copy will be placed in the patient's medical record.

5.2.2 Waiver of Documentation of Consent (Implied consent, Verbal consent, etc.)

A waiver of documentation of consent is being requested for use of the phone screening process. During phone contact with a potential participant, verbal consent is obtained from the caller in order for the study coordinator to continue explaining the research study and asking pertinent eligibility questions. If the caller is interested in participating in this study, a study visit will be scheduled.

5.3 Consent – Other Considerations

After the consent is obtained, 1 ml of blood will be drawn and sent to the clinical laboratory for measurement of kidney function as base line creatinine level. Once the creatinine level is known and found to be within normal limits, they will be included in to the study. Once included they will be informed of the date and time of the study and advised to fast from solids for at least 6 hours prior to the study, with clear liquid permitted until 2 hours before the procedure.

6.0 HIPAA Research Authorization and/or Waiver or Alteration of Authorization

6.1 Authorization and/or Waiver or Alteration of Authorization for the Uses and Disclosures of PHI

Check all that apply:

- ☐ Not applicable, no identifiable protected health information (PHI) is accessed, used or disclosed in this study. *[Mark all parts of sections 6.2 and 6.3 as not applicable]*
- ☒ Authorization will be obtained and documented as part of the consent process. *[If this is the only box checked, mark sections 6.2 and 6.3 as not applicable]*
- ☐ Partial waiver is requested for recruitment purposes only (Check this box if patients' medical records will be accessed to determine eligibility before consent/authorization has been obtained). *[Complete all parts of sections 6.2 and 6.3]*
- ☐ Full waiver is requested for entire research study (e.g., medical record review studies). *[Complete all parts of sections 6.2 and 6.3]*
- ☒ Alteration is requested to waive requirement for written documentation of authorization (verbal authorization will be obtained). *[Complete all parts of sections 6.2 and 6.3]*

